IUD	Intrauterine device
IUS	Intrauterine hormone-releasing system
KCTU	King's Clinical Trials Unit
KHP-CTO	King's Health Partners-Clinical Trials Office
LFT	Liver Function test
MOAS	Modified Overt Aggression Scale
MHRA	Medicines & Healthcare Regulatory Agency
NICE	National Institute for Health and Care Excellence
NIHR	National Institute of Health Research
OTC	Over the counter
PANSS	Positive and Negative Syndrome Scale
PIN	Patient Identification Number
PO	Per oral
POMH-UK	Prescribing Observatory for Mental Health – UK
QALYS	Quality-adjusted life years
QP	Qualified person
REC	Research Ethics Committee

RCT	Randomised controlled trial
SAE	Serious Adverse Event
SAP	Statistical Analysis Plan
SAR	Serious Adverse Reaction
SCID	Structured Clinical Interview for DSM-5
SF-36	36-Item Short Form Survey
sIMPD	Simplified Investigational Medicinal Product Dossier
SmPC	Summary of Product Characteristics
SOP	Standard Operating Procedure
SUSAR	Suspected Unexpected Serious Adverse Reaction
SWEMWBS	Short Warwick-Edinburgh Well-being scale
TBC	Total Blood Count
TMG	Trial Management Group
TRS	Treatment resistant schizophrenia
TSC	Trial Steering Committee
UAR	Unexpected Adverse Reaction
UKU	Udvalg for Kliniske Undersogelser (side effect rating scale)
USAR	Unexpected serious adverse reaction
YMRS	Young Mania Rating Scale

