9.2 Procedures for Recording and Reporting Adverse Events

The Medicines for Human Use (Clinical Trials) Regulations 2004 and Amended Regulations 2006 gives the following definitions:

Averse Event (AE): Any untoward medical occurrence in a subject to whom a medicinal product has been administered including occurrences which are not necessarily caused by or related to that product.

Adverse Reaction (AR): Any untoward and unintended response in a subject to an investigational medicinal product which is related to any dose administered to that subject.

Unexpected Adverse Reaction (UAR): An adverse reaction the nature and severity of which is not consistent with the information about the medicinal product in question set out in the summary of product characteristics (SmPC) for that product.

Serious adverse Event (SAE), Serious Adverse Reaction (SAR) or Unexpected Serious Adverse Reaction (USAR): Any adverse event, adverse reaction or unexpected adverse reaction, respectively, that

- Results in death;
- Is life-threatening;
- Required hospitalisation or prolongation of existing hospitalisation;
- Results in persistent or significant disability or incapacity;
- Consists of a congenital anomaly or birth defect.

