Appendix 2 gives a schematic of AE categorization and reporting procedure.

Important Medical Events (IME) & Pregnancy

Events that may not be immediately life-threatening or result in death or hospitalisation but may jeopardise the patient or may require intervention to prevent one of the other outcomes listed in the definition above should also be considered serious.

During the study, if the subject has a hospitalization procedure (e.g. elective surgery) that was scheduled before the study entry, i.e. before consent for an event/condition that occurred before the study, the hospitalization is considered a therapeutic intervention and not the result of SAE. However, if the event/condition worsens during the study, it should be reported as an AE (of SAE if the outcome so warrants).

Although not a serious adverse event, any unplanned pregnancy will also be reported via the SAE reporting system. Each pregnancy will be followed up until the outcome is

known. The CI or PI will liaise with the relevant obstetrician throughout the pregnancy. In the event of a congenital anomaly or birth defect detected in the foetus or live born child it will be reported as an SAE. The database record of all pregnancies will be held by the KHP-CTO, this will include follow up to term and where appropriate, long-term follow up of the baby.

Urgent safety measures

Regulations allow the sponsor and investigator to take appropriate urgent safety measures to protect clinical trial subjects from any immediate hazard to their health and safety. The CI must inform the KHP-CTO as soon as possible after the implementation of the urgent safety measures. The CI or sponsor will phone the MHRA's clinical trial unit on [name] to discuss the issue with a safety scientist, ideally within 24 hours. The MHRA will inform the CI or Sponsor how the submit the substantial amendment to them within 3 days when spoken to them but instructions will be sent by email. The sponsor will then notify the MHRA and the REC in writing, of the measures taken and the reason for the measures within 3 days by submitting a substantial amendment. The decision to undertake appropriate safety measures may be taken by:

- The CI and/or PI
- The KHP-CTO on behalf of the sponsor and in consultation with the CI or DMC

Ongoing safety

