9.2.1 Adverse events that do not require reporting

Events or reactions listed in the SmPC of Sodium valproate or that of the antipsychotic drug will not be reported. The period for AE reporting will be from screening until 60 days post final IMP administration.

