Appendix 2 - SAE Reporting schematic

The **AE** event is **SERIOUS** if any of the following criteria applies:

- 1. The participant died
- 2. The participant was at risk of death because of the AE
- 3. The AE lead to admission or extension of admission to hospital
- 4. The AE resulted in persistent or significant disability/incapacity
- 5. The AE is an important medical event that may jeopardise the participant (or an unborn child) and may require medical or surgical intervention to prevent one of the outcomes listed above

The event should be classed as a **SUSPECTED ADVERSE REACTION** if a possible relationship with the IMP cannot be ruled out.

If the nature of the adverse reaction is consistent with the SmPC or other relevant product information of the IMP or antipsychotic medication, then the event should be classed as an UNEXPECTED REACTION.

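### Appendix 2 states the expectedness test the opposite way round from Section 9.2, so SUSAR classification is reversed wherever staff apply the appendix as written

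*Protocol*

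**What the plan says.** Section 9.2 of the protocol gives the definitions, which it attributes to the UK clinical trials regulations. An unexpected adverse reaction is "An adverse reaction the nature and severity of which is not consistent with the information about the medicinal product in question", with the SmPC for that product as the source of that information.

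The text that follows these definitions sends the reader to the appendix: "Appendix 2 gives a schematic of AE categorization and reporting procedure". Appendix 2 takes seriousness, then causality, then expectedness. Its expectedness step opens with "If the nature of the adverse reaction is consistent with the SmPC" and, after offering other sources as an alternative to the SmPC, continues "product information of the IMP or antipsychotic medication, then the event should be classed as an UNEXPECTED REACTION".

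Three other places bear on this:

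- Section 5.3 names the SmPC for the sodium valproate 500 mg gastro-resistant tablet as the reference document.
- Section 9.2.1 says: "Events or reactions listed in the SmPC of Sodium valproate or that of the antipsychotic drug will not be reported".
- Section 9.2, under reporting responsibilities, sets 7 days for fatal or life-threatening SUSARs and 15 days for the others. It also requires investigators to send every SAE, SAR and SUSAR to the KHP-CTO and the chief investigator within 24 hours. The KHP-CTO then reports SUSARs to the MHRA, and the chief investigator reports to the ethics committee.

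**The concern.** The definition and the schematic give opposite answers to the same question. The schematic is the part that site staff are likely to have in front of them when they complete an SAE form.

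Expectedness is not a descriptive label here. The glossary expands SUSAR as "Suspected Unexpected Serious Adverse Reaction", so the unexpected element is what separates a serious suspected reaction on an expedited clock from one that is not. If it is turned round, effort goes into expediting reactions already in the SmPC. The reactions at risk of missing the clock are those the SmPC does not describe, which are the ones expedited reporting is meant to catch.

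Two smaller differences would survive a correction of the inverted word alone. Appendix 2 tests nature only, while Section 9.2 tests nature and severity. Appendix 2 also admits the antipsychotic's product information, while Section 9.2 speaks of the product in question and Section 5.3 names the valproate SmPC.

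**Working it through.** No arithmetic applies: the point depends on no sample size, error rate or event count. The check sets the texts side by side for a reaction that is already judged serious and suspected to be related to the IMP.

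| Reaction | Section 9.2 | Appendix 2 as written |
|---|---|---|
| Consistent with the SmPC | Not unexpected, so not a SUSAR | Unexpected (stated), so a SUSAR with a 7- or 15-day report |
| Not consistent with the SmPC | Unexpected, so a SUSAR with a 7- or 15-day report | No class stated; by implication not unexpected, so not a SUSAR |

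1. **First row.** The conflict is explicit. The same reaction cannot be both unexpected and not unexpected, so the two texts cannot both be followed.
2. **Second row.** The conflict is by implication. Appendix 2 gives a class only to reactions that agree with the product information. A reader who takes its rule as the whole test will treat the rest as expected.
3. **Section 9.2.1.** For the first row it adds a third answer. Listed reactions are not to be reported, although Appendix 2 would make the serious suspected ones SUSARs. Section 9.2.1 does not say whether it is limited to non-serious events. If it is not, it also conflicts with the 24-hour duty in Section 9.2, which covers all SAEs.
4. **Severity.** Take a reaction listed in the SmPC that occurs in a more severe form than is listed. Section 9.2 asks about severity as well as nature. Appendix 2 asks about nature only, so with the inversion corrected and nothing else changed it would pass this reaction as expected.
5. **Reference document.** Take a serious reaction suspected to be due to valproate that is absent from the valproate SmPC but listed for the background antipsychotic. Under Sections 5.3 and 9.2 it is unexpected. Under Appendix 2 with only the inversion corrected it would be expected. Section 9.2.1 also refers to the antipsychotic's SmPC, so the wider reference is not peculiar to the appendix.

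**The case against.** The strongest reply is that the protocol holds the correct definition and a safeguard that does not depend on the appendix. Section 9.2 states expectedness the right way round. Every SAE goes to the KHP-CTO and the chief investigator within 24 hours whatever its expectedness, for review under a pharmacovigilance policy, and it is the KHP-CTO, not the site, that reports SUSARs to the MHRA. A novel serious reaction should therefore still reach people who can classify it correctly.

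This stands as a limit on size. A reader might infer that every suspected serious reaction in the trial would be misclassified and that new ones would never be expedited. The documents do not support that. The reversal occurs only where Appendix 2 is applied in place of Section 9.2, half of it is implied and not stated, and the policy that governs the central review is not shown. The reply does not excuse the error, because the central review starts from a form completed under instructions that contradict the protocol's own definition, and nothing shown says which text prevails.

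A second reply is that a *not* or a branch of a diagram was lost when the PDF was read. This cannot be fully excluded, since the appendix is called a schematic. The sentence is nevertheless complete and grammatical with no sign of a gap, so it is taken as it stands. A look at the source document would settle it.

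**Conclusion.** The contradiction is real and sits in operative safety text. Appendix 2 classes as unexpected what Section 9.2 defines as not unexpected, and Section 9.2 points to Appendix 2 for categorisation. Its size is a risk, not a count: where the appendix is followed as written, listed serious suspected reactions become SUSARs, and unlisted ones by implication do not. The 24-hour central reporting lowers the chance that a novel reaction misses its 7- or 15-day report, but does not remove it.

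The conclusion assumes that the appendix sentence was read correctly from the PDF and that some staff work from the schematic. It does not touch the estimand, randomisation, power or efficacy analysis. It is an internal inconsistency, most likely a drafting slip, but it should be corrected without delay because expedited reporting depends on the rule and the correction is small.

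**What to change.** 1. In Appendix 2, insert the missing *not* and add severity, so that the expectedness step carries the Section 9.2 definition. Repeating that definition word for word avoids creating a new variant.
2. In the same edit, reconcile Sections 5.3, 9.2 and 9.2.1 and Appendix 2 on which product information is the reference for expectedness: the valproate SmPC only, or the antipsychotic's as well. Deleting the antipsychotic from Appendix 2 alone would leave it at odds with Section 9.2.1, so the sponsor should decide once and use the same wording throughout.
3. State in Section 9.2.1 which events it exempts and from which report, so that it fits with the 24-hour duty for all SAEs.
4. Notify sites of the corrected schematic.

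The cost is one sentence in the appendix, consistent wording in the sections named, and a note to sites. No data collection, sample size or analysis changes.
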